8. GENERAL ISSUES FOR STATISTICAL ANALYSES

8.1 Adjustment for Covariates

Not applicable.

Summary tables will show unadjusted GMCs for each vaccine group and unadjusted ratios of GMCs.

Binary data tables will show unadjusted percentages.

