1.1 Background

This GVGH *S. sonnei* 1790GAHB vaccine has been tested in two Phase 1 trials in European adult population: H03_01TP, looking at the intramuscular (IM) administration,

and H03_02TP, looking at the intradermal (ID), intranasal (IN) and IM administration. Based on the results from these phase 1 studies, it has been decided to proceed with further development using only the IM route of immunization and to test in the proposed H03_04TP study two doses selected based on the results from H03_01TP study. The two doses have been selected as follows: 25 µg is the lowest dose that in phase 1 induced antibody titers comparable to antibodies in a population of convalescent subjects after natural infection already after the first vaccination, while 100 µg is tested for two reasons i.e.1) a higher dose may be needed to induce high antibody titers in endemic population and 2) there is a need to test in African populations the tolerability of a higher dose of GMMA that will be ultimately needed in the multivalent vaccine against Shigellosis.

The proposed H03_04TP trial is the logical continuation of the two Phase 1 studies and is aimed to evaluate the safety and immunogenicity profile of 1790GAHB in adults from an African country, where shigellosis remains a major health problem.

The dose regimen tested in phase 1 studies (three doses given 1 month apart) did not show any significant benefit from the third dose in terms of immunogenicity, therefore a two dose schedule was selected for the current trial. The two dose schedule will allow evaluation of the immunogenicity in the endemic population where one dose may be not enough to induce the same immunogenicity observed in European population.

During the two phase 1 trials two subjects of African descent experienced a transient and clinically asymptomatic decrease of circulating neutrophils of grade 3 (severe) that was finally classified as "benign ethnic neutropenia". In addition, six more subjects experienced transient and clinically asymptomatic grade 2 (moderate) neutropenia. Although this finding was not associated with any clinical illness, some precautionary procedures for enrollment and monitoring of trial subjects have been introduced to protect the safety of study subjects (refer to [Section 3.7, Procedures Related to Neutropenia](#)).

The trial will be conducted in compliance with the protocol, GCP and applicable regulatory requirement(s).

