3. STUDY DESIGN

This is a phase 2a, randomized, controlled, single center, observer blind trial that will enroll approximately 72 healthy adult subjects, 18-45 years of age inclusive.

As currently there is no vaccine available against shigellosis, the safety of the 1790GAHB vaccine will be evaluated against two licensed control vaccines: one dose of Menveo as 1st injection and one dose of Boostrix as 2nd injection.

Subjects will be randomized to one of the three parallel treatment arms in a 1:1:1 ratio to receive either the study vaccine dose A (25 µg), the study vaccine dose B (100 µg) or the control vaccines as follows:

Table 3-1 Overview of the Study Groups

	No. Subjects
Group A (25 µg)	24
Group B (100 µg)	24
Group C (Control)	24
Total	72

Two injections of the study vaccine or the two control vaccines will be administered 28 days apart.

The study includes a screening visit (performed at study Days -28/-1), five Clinical Visits (performed at study Day 1, 7, and 28 days after 1st injection and 7 and 28 days after 2nd injection) and daily home visits performed for 6 days after the 1st and 2nd injection.

Blood (approximately 10 mL) will be drawn from all subjects before the first injection (visit 1), 28 days after the first injection (visit 3), and 28 days after the second injection (visit 5) for immunogenicity evaluation.

Appropriately trained study staff will be instructed to complete the subject's diary card during daily home visits following discussion with the subject to (i) describe solicited local (i.e. injection site erythema, induration and pain) and systemic (i.e. fever [temperature $\geq 38.0^{\circ}\text{C}$ measured axillary], fatigue, malaise, myalgia, chills, arthralgia and headache) adverse events (AEs) occurring during the day of each injection visit (visit 1 and 3) and for the following 6 days; (ii) indicate if any analgesic/antipyretic to prevent or treat pain/fever was taken after injection.

In addition to the solicited adverse events data, from study visit 1 through visit 5 (i.e. study termination visit) any unsolicited AE, all serious adverse events (SAEs), all AEs

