8.7 Data Transformation

Distributions of antibodies are generally skewed to the right (Nauta, 2010). Therefore, prior to any statistical analysis that assumes normally distributed observations, antibody titers or concentrations will be \log_{10} -transformed. GMTs [/GMCs] and their 95% CIs are computed by exponentiating (base 10) the least squares means and 95% CIs of the \log_{10} titers.

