8.8 Derived and Computed Variables

Demographics

Age will be calculated in years using the following formula:

$$(\text{Date of Visit 1} - \text{Date of Birth} + 1) / 365.25$$

Body Mass Index (kg/m²) will be calculated using the following formula:

$$\text{Weight (kg)} / \text{Height}^2 (\text{m}^2)$$

Immunogenicity

Values below the limit of quantification (recorded as “< LQ”) will be set to half that limit (i.e., LQ/2].

Seroresponse is defined for subjects with non-missing values pre-vaccination and post-vaccination as:

If the baseline value is greater than 50 EU then an increase of at least 50% in the post-vaccination sample as compared to baseline [i.e. $((\text{Post-vac minus baseline})/\text{baseline})100\% \geq 50\%$]

If the baseline value is less or equal to 50 EU then an increase of at least 25 EU in the post-vaccination sample as compared to baseline [i.e. $(\text{post-vac minus baseline}) \geq 25 \text{ EU}$]

High seroresponse is defined for subjects with non-missing post-vaccination as:

Post vaccination titer ≥ 121 anti-LPS serum IgG units in the GSK ELISA

Geometric Mean Concentration

The GMC will be calculated using the following formula:

$$10^{\left\{ \frac{\sum_{i=1}^n \log_{10}(t_i)}{n} \right\}}$$

where t_1, t_2, \dots, t_n are n observed immunogenicity titers/concentrations.

Geometric Mean Ratio

Geometric mean ratios (GMRs) measure the changes in immunogenicity titers/concentrations *within* subjects.

The GMR will be calculated using the following formula:

$$10^{\left\{ \frac{\sum_{i=1}^n \log_{10}\left(\frac{v_{ij}}{v_{ik}}\right)}{n} \right\}} = 10^{\left\{ \frac{\sum_{i=1}^n \log_{10}(v_{ij}) - \log_{10}(v_{ik})}{n} \right\}}$$

where, for n subjects, v_{ij} and v_{ik} are observed immunogenicity titers/concentrations for subject i at time-points j and k , $j \neq k$.

Duration in the Study

Duration in the study is defined in days as:

Last visit date (visit x)^a – Enrollment date (visit 1) + 1

^aor premature discontinuation date (in case of withdrawal from the study)

The duration is missing if one of the dates is missing or incomplete.

Solicited Adverse Events

For details see [section 13.2](#).

Unsolicited Adverse Events

All adverse events will be characterized according to the date of occurrence related to the vaccination phase as follows:

- **Emergence before vaccination phase:** start date before the first date of injection of study vaccine.

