 - A post vaccination concentration ≥ 121 anti-LPS serum IgG units in the GVGH ELISA corresponds to a titer of 1:800 in the ELISA method used by Cohen et al. (1989 J. Clin. Microbiol. 27:162). This antibody level is the median antibody concentration of a set of 87 convalescent subjects previously infected by *S. sonnei*. The value of 121 anti-LPS serum IgG units in the GVGH ELISA was determined by calibration against the Cohen ELISA (i.e., the GVGH standard serum was tested in Cohen's lab using the Cohen's methodology).

Statistical hypothesis:

This Phase 2a safety and immunogenicity trial is aimed to descriptively evaluate the safety and immunogenicity profiles of the study vaccines. No specific hypotheses are tested in this trial.

Statistical models:

GMCs

The ELISA concentrations will be logarithmically transformed (base10) (to fulfil the normal distribution assumption). For each treatment group, GMC will be calculated, with their associated two-sided 95% CIs, by exponentiating the corresponding log-transformed means and their 95% CI.

Additionally, within-subject GMRs will be computed for GMTs/GMCs at one month after first, and second vaccination versus baseline (day 1). The GMRs and 95% CIs will be constructed by exponentiating the mean within-subject differences in log-transformed titers and the corresponding 95% CIs.

Analysis of binary variables:

The number and percentages of subjects with seroresponse and with high seroresponse in ELISA concentrations from baseline, will be summarized. Two-sided 95% Clopper-Pearson CIs for the percentages will be computed.

Titers below the limit of detection will be set to half that limit for the purposes of analysis. Missing values of immunogenicity will be excluded from analyses (i.e. complete-case analysis) since they are considered missing completely at random, i.e. not informative and with no impact on inferences.

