17. LIST OF FINAL REPORT TABLES, LISTINGS AND FIGURES

For the complete list of tables, listings and figures, please refer to the Table of Contents (TOC). Note that a listing of individual efficacy/immunogenicity lab data (see “Other TOC” tab in the TOC) will be created, to allow data dissemination to the study subjects. This listing will show the following data:

- Subject ID
- Actual vaccine(s) received by the subject
- Lab results for immunogenicity safety at each visit.

This listing is mentioned in the tab “Other TOC” in the TOC and will not be part of the CSR stat package.

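### Report a Day 1-adjusted GMC ratio beside each unadjusted ratio: a modest precision gain from data already collected, in a descriptive secondary objective

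*SAP*

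**What the plan says.** SAP 8.1 marks adjustment for covariates as not applicable and states: "Summary tables will show unadjusted GMCs for each vaccine group and unadjusted ratios of GMCs". It gives no contrast, time point or confidence interval for those ratios, and neither SAP 11.3 nor protocol 8.4.3.3.3 supplies them.

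The word ratio has a separate defined use. SAP 8.8 says "Geometric mean ratios (GMRs) measure the changes in immunogenicity titers/concentrations" within subjects, and SAP 11.3 plans these GMRs against Day 1 with 95% CIs. SAP 8.7 says that GMCs are "computed by exponentiating (base 10) the least squares means and 95% CIs" of the log10 titers, but no model is named that would produce least squares means.

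The covariate exists for everyone. SAP 3 says "Blood (approximately 10 mL) will be drawn from all subjects before the first injection (visit 1"), and the Day 1 GMC is itself a listed measure.

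Two wording points lie nearby. The half-limit rule in SAP 8.8 applies to "Values below the limit of quantification", while SAP 11.3 says "Titers below the limit of detection will be set to half that limit for the purposes of analysis"; protocol 8.4.3.3.3 also uses the detection limit, as do the strata of endpoints (d) and (e). And SAP 11.3 describes high seroresponse as relative to baseline, while SAP 8.8 and protocol 8.4.3.3.3 define it on the post-vaccination level alone.

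**The concern.** The immunogenicity result of this trial is a set of estimates and intervals, with about 20 evaluable subjects per arm. One of the protocol's two reasons for testing 100 µg is that "a higher dose may be needed to induce high antibody titers in endemic population" (protocol 1.1). The 100 versus 25 µg GMC ratio describes that directly.

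Subjects in an endemic area may carry antibody at Day 1: exclusion criterion 20 removes only previous laboratory-confirmed *S. sonnei* disease. In arms this small, Day 1 levels can differ by chance, and an unadjusted ratio carries that difference into the post-vaccination comparison as noise. Part of it can be removed with a measurement the trial already takes. What is at stake is the width of the interval.

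**Working it through.** **Inputs.** The plan states no precision figure for IgG. Its only sample-size figures are in the protocol synopsis, and they reproduce: 1 - 0.9^20 = 0.878 (87% stated), and 20/(1 - 0.15) = 23.5, so 24 enrolled per arm for 20 evaluable. I take n = 20 per arm. The documents give neither the SD of log10 IgG nor rho. I assume SD = 0.5, equal at Day 1 and after vaccination, and show rho from 0 to 0.8.

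**Half-widths on the log10 scale for one two-arm contrast**

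- Unadjusted: t(38) × SD × sqrt(2/n) = 2.024 × 0.5 × 0.3162 = 0.320. The 95% CI factor is 10^0.320 = 2.09.
- Ratio of the two arms' within-subject GMRs: the unadjusted half-width × sqrt(2(1 - rho)). At rho 0.7: 0.320 × 0.7746 = 0.248, factor 1.77.
- ANCOVA on the two arms: t(37) × SD × sqrt(1 - rho²) × sqrt(2/n) × sqrt(1 + 1/(2n - 4)). At rho 0.5: 2.026 × 0.5 × 0.866 × 0.3162 × 1.014 = 0.281, factor 1.91.

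| rho | Unadjusted | Ratio of GMRs | ANCOVA | ANCOVA log CI vs unadjusted | vs the tighter of the two |
|---|---|---|---|---|---|
| 0 | 2.09 | 2.84 | 2.11 | 1.5% wider | 1.5% wider |
| 0.3 | 2.09 | 2.39 | 2.04 | 3% narrower | 3% narrower |
| 0.5 | 2.09 | 2.09 | 1.91 | 12% narrower | 12% narrower |
| 0.7 | 2.09 | 1.77 | 1.71 | 27-28% narrower | 6% narrower |
| 0.8 | 2.09 | 1.59 | 1.57 | 39% narrower | 4% narrower |

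The last column peaks at rho 0.5. Below that the unadjusted ratio is the tighter comparator and the gain rises with rho. Above it the ratio of GMRs is tighter, and the relative width is sqrt((1 + rho)/2) apart from the small degrees-of-freedom penalty, so the gain falls again.

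**Sensitivity.** The relative widths do not depend on the SD; the factors do. At SD 0.3 the unadjusted, rho 0.5 and rho 0.7 factors are 1.56, 1.47 and 1.38; at SD 0.7 they are 2.81, 2.48 and 2.11. The break-even rho against the unadjusted ratio is about 0.16. If 50% of baselines fall below the assay limit and are set to half of it (assumed), the gain over the unadjusted ratio at rho 0.5, 0.7 and 0.8 falls to 9%, 21% and 30%.

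**Simulation check of the two-arm ANCOVA** (20,000 runs per setting, rho 0 to 0.7, including 30% of baselines at half the limit and unequal slopes): bias at most 0.003 log10, coverage 94.6-95.2%.

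**Why two arms per fit.** Controls may track their baseline more closely than vaccinees. With an assumed rho of 0.95 in controls and 0 to 0.7 in the vaccine arms (10,000 runs each), one pooled three-arm ANCOVA covered 91.0-92.4% for 100 versus 25 µg, against 94.8-95.2% for the two-arm fit. For 25 µg versus control the two-arm fit covered 94.5-94.7%.

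**The case against.** The case for leaving the plan alone is substantial.

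- *No planned question depends on it.* The trial tests no hypotheses and has no success criteria. Endpoints (a) to (e) are all per-group summaries, and no objective or endpoint names a between-arm IgG contrast. This stands, and limits the point to an improvement.
- *The between-group reading of SAP 8.1 is inferred.* This also stands: the only ratio the endpoints define is post- over pre-vaccination. The separate output list might settle it (SAP 17: "For the complete list of tables, listings and figures, please refer to the Table of Contents (TOC")), but it is not among the documents. The contrasts need naming under either reading.
- *Day 1 IgG is already used.* A reader might infer that the SAP ignores baseline. It does not: it plans within-subject GMRs, a baseline-relative seroresponse, and summaries split by baseline status. None of these is an adjusted between-arm ratio, and a ratio of GMRs is wider than the unadjusted ratio when rho is below 0.5.
- *The large gains use the weaker comparator.* The 27-28% and 39% hold only against the unadjusted ratio. A ratio of GMRs is not itself specified, but its components are planned.
- *Rho may be low where it matters most.* If vaccinees track baseline less closely than controls, 100 versus 25 µg may sit at rho 0 to 0.3, where the result runs from 1.5% wider to 3% narrower. The documents cannot settle this.
- *Separate two-arm fits are not one coherent model.* They give each arm two adjusted means, and the three ratios need not multiply through. The fits should therefore supply ratios only.

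**Conclusion.** The point holds as a no-cost improvement in precision for a descriptive secondary objective. Nothing in SAP 8.1, SAP 11.3 or protocol 8.4.3.3.3 yields a Day 1-adjusted between-arm ratio, and the data for one are already planned. At 20 per arm the worst case is a log interval 1.5% wider; the best case over the tighter available summary is about 12% narrower, with 4-6% at rho 0.7-0.8. These figures rest on an assumed rho and on equal SDs at Day 1 and after vaccination, and they shrink if many baselines lie below the assay limit.

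Two stronger readings are not supported. The unadjusted ratio is not biased, because arms are randomised 1:1:1. And no trial conclusion is at risk, because none is tied to this contrast.

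The limit wording and the high-seroresponse wording are separate minor items. The limit wording could change imputed values and strata if the two limits differ; the seroresponse wording has little effect, because SAP 8.8 and endpoint (c) already fix the definition.

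**What to change.** Keep every unadjusted table. In SAP 8.1 and 11.3:

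1. Name the contrasts: 100 versus 25 µg, and each dose versus control, at Visit 3 and at Visit 5.
2. Beside each unadjusted ratio, report a Day 1-adjusted GMC ratio with 95% CI from an ANCOVA of log10 IgG on group and log10 Day 1 IgG, fitted on the two arms compared.
3. Use these fits for ratios only. Group GMCs stay unadjusted and are not taken from these models.
4. Leave subjects without a Day 1 result out of the adjusted ratio; the FAS definition in SAP 7.3 requires only post-vaccination data, so a rule is needed. Values below the assay limit enter the covariate at half the limit.
5. Fix the model before the group-unblinded preliminary immunogenicity analysis in protocol 8.6 (version 4.0). SAP 14.1 still says that no interim analysis is planned, so the deadline must be taken from the protocol.

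Separately, use one limit (quantification or detection) in SAP 8.8, SAP 11.3, protocol 8.4.3.3.3 and the (d)/(e) strata, and delete the reference to baseline for high seroresponse in SAP 11.3.

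Cost: SAP wording and one descriptive table, with no new samples or visits. The adjusted ratio spends one degree of freedom, assumes a linear relation on the log10 scale, and need not multiply through exactly across the three contrasts.

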8.2 Handling of Dropouts, Missing Data

First-line analyses will be without missing values.

8.2.1 Safety Data

Solicited adverse events: The solicited study period will be '30 min - day7'.

No imputation methods will be used to address missing values.

Unsolicited adverse events: The unsolicited adverse events will be analyzed in the entire study period.

8.2.2 Immunogenicity Data

Missing immunogenicity values are considered MCAR and therefore will not contain information that impact the result of the analysis (i.e., not informative). Imputation methods will therefore not be used. The immunogenicity objectives will be analyzed using the modified FAS.

8.2.3 Efficacy Data

Not applicable.

8.3 Multicenter Studies

Not applicable as this is a single center study.

To be included in section 11.4.2.4 of the CSR and not part of the SAP.

Subjects were recruited in one center only.

8.4 Multiple Comparisons and Multiplicity

Statistical analyses will only be used for descriptive purposes therefore no multiplicity adjustment will be done.

To be included in section 11.4.2.5 of CSR and not part of the SAP.

Statistical analyses were only used for descriptive purposes therefore no multiplicity adjustment was made.

8.5 Immunogenicity Subsets

Not applicable. All subjects will be evaluated for the immunogenicity analysis.

8.6 Subgroups

Not applicable.

8.7 Data Transformation

Distributions of antibodies are generally skewed to the right (Nauta, 2010). Therefore, prior to any statistical analysis that assumes normally distributed observations, antibody titers or concentrations will be \log_{10} -transformed. GMTs [/GMCs] and their 95% CIs are computed by exponentiating (base 10) the least squares means and 95% CIs of the \log_{10} titers.

8.8 Derived and Computed Variables

Demographics

Age will be calculated in years using the following formula:

$$(\text{Date of Visit 1} - \text{Date of Birth} + 1) / 365.25$$

Body Mass Index (kg/m²) will be calculated using the following formula:

$$\text{Weight (kg)} / \text{Height}^2 (\text{m}^2)$$

Immunogenicity

Values below the limit of quantification (recorded as “< LQ”) will be set to half that limit (i.e., LQ/2].

Seroresponse is defined for subjects with non-missing values pre-vaccination and post-vaccination as:

If the baseline value is greater than 50 EU then an increase of at least 50% in the post-vaccination sample as compared to baseline [i.e. $((\text{Post-vac minus baseline})/\text{baseline})100\% \geq 50\%$]

If the baseline value is less or equal to 50 EU then an increase of at least 25 EU in the post-vaccination sample as compared to baseline [i.e. $(\text{post-vac minus baseline}) \geq 25 \text{ EU}$]

High seroresponse is defined for subjects with non-missing post-vaccination as:

Post vaccination titer ≥ 121 anti-LPS serum IgG units in the GSK ELISA

Geometric Mean Concentration

The GMC will be calculated using the following formula:

$$10^{\left\{ \frac{\sum_{i=1}^n \log_{10}(t_i)}{n} \right\}}$$

where t_1, t_2, \dots, t_n are n observed immunogenicity titers/concentrations.

Geometric Mean Ratio

Geometric mean ratios (GMRs) measure the changes in immunogenicity titers/concentrations *within* subjects.

The GMR will be calculated using the following formula:

$$10^{\left\{ \frac{\sum_{i=1}^n \log_{10}\left(\frac{v_{ij}}{v_{ik}}\right)}{n} \right\}} = 10^{\left\{ \frac{\sum_{i=1}^n \log_{10}(v_{ij}) - \log_{10}(v_{ik})}{n} \right\}}$$

where, for n subjects, v_{ij} and v_{ik} are observed immunogenicity titers/concentrations for subject i at time-points j and k , $j \neq k$.

Duration in the Study

Duration in the study is defined in days as:

Last visit date (visit x)^a – Enrollment date (visit 1) + 1

^aor premature discontinuation date (in case of withdrawal from the study)

The duration is missing if one of the dates is missing or incomplete.

Solicited Adverse Events

For details see [section 13.2](#).

Unsolicited Adverse Events

All adverse events will be characterized according to the date of occurrence related to the vaccination phase as follows:

- **Emergence before vaccination phase:** start date before the first date of injection of study vaccine.
- **Emergence during vaccination phase:** start date on or after the first date of injection of study vaccine or, adverse event increase in severity including to “serious” adverse event.

If start date is equal to the first date of injection then “timing” variable (“On injection day, before injection”/“On injection day, after injection”) will be used to define whether the adverse event occur before or after the injection.

If there are several vaccinations, the adverse event will be associated with the most recent vaccination.

If an adverse event start date is missing or unknown, the adverse event will be considered as emergent.

When start and/or end dates of an adverse event are only partially known, adverse events will be categorized as emergent before, during, or after vaccination phase using the following rules:

- If the partial end date is before ($<$) the first study vaccination (i.e., year or year & month is/are before the first study vaccination year or year & month) then the adverse event is emergent before vaccination phase.
- If the partial start date is equal or after (\geq) the first study vaccination (i.e., year or year & month is/are after or the same as the first study injection year or year & month) then the adverse event is emergent during vaccination phase.

The **maximum event severity** is the greatest severity associated with a preferred term for a reported adverse event according to the following order: Mild < Moderate < Severe. Unknown/ Missing severity is considered as severe (except for the definition of emergence).

Multiple AEs with the same PT for the same subject are counted only once.

Vaccination-related Adverse Events are those for which the cause has been evaluated by the investigator, and recorded either as possibly related, probably related or unknown/missing.

Safety Laboratory Data

All laboratory measurements summarized in the CSR are those defined in the study protocol.

Reference ranges used to categorize the results as “low” (values below the lower limit of the reference range), “normal” (values within the reference range) or “high” (values above the upper value of the reference range) will be those provided by the site lab which performed the tests and provided the laboratory reports.

Prestudy, Concomitant and Post-Vaccination Medications

A **previous medication** is a medication used only before the first study vaccination (i.e. medication end date < first study vaccination date).

All other medications are **concomitant**.

When start and/or end dates of a medication intake are missing, the medication is considered as concomitant with the study vaccination schedule.

If the first study vaccination date is missing then the medication is considered as concomitant with the study vaccination schedule, provided that the study vaccine was administered to the subject.

For further details please refer to the technical and program specifications document stored in Home/analysis/H03_01TP/final/prod/docs within the SAS Drug Development (SDD) server.

